### **A4-1.5 EMBRYOFETAL TOXICITY**

Administration of tiragolumab is expected to have adverse effects on pregnancy based on the expression of TIGIT on decidual NK and CD8+ T cells (Powell et al. 2017; van der Zwan et al. 2018; Vento-Tormo et al. 2018), and the expected role of these cells in the recognition and response to foreign fetal, placental, and viral antigens at the maternal-fetal interface as well as maintenance of maternal-fetal tolerance. No reproductive or teratogenicity studies in animals have been conducted with tiragolumab. There are no clinical studies of tiragolumab in pregnant women. Tiragolumab should not be administered to pregnant women.

Refer to Section 6 of the Tiragolumab Investigator's Brochure for a detailed description of embryofetal toxicity.

### **A4-2 RISK ASSOCIATED WITH ATEZOLIZUMAB**

Atezolizumab has been associated with risks such as the following: IRRs and immune-mediated hepatitis, pneumonitis, colitis, pancreatitis, diabetes mellitus, hypothyroidism, hyperthyroidism, adrenal insufficiency, hypophysitis, Guillain-Barré syndrome, myasthenic syndrome or myasthenia gravis, facial paresis, myelitis, meningoencephalitis, myocarditis, pericardial disorders, nephritis, myositis, and severe cutaneous adverse reactions. In addition, immune-mediated reactions may involve any organ system and may lead to hemophagocytic lymphohistiocytosis (HLH). Refer to Section [A4-5.3](#) of the protocol and Section 6 of the Atezolizumab Investigator's Brochure for a detailed description of anticipated safety risks for atezolizumab.

### **A4-3 RISK ASSOCIATED WITH COMBINATION USE OF TIRAGOLUMAB AND ATEZOLIZUMAB**

Based on results from clinical data with tiragolumab plus atezolizumab, there are known and potential overlapping toxicities in participants treated with tiragolumab plus atezolizumab. Because the expected pharmacologic activity of these two molecules is to increase adaptive T-cell immune responses, there is the possibility of heightened immune responses.

Refer to Section 6 of the Tiragolumab Investigator's Brochure for a list of identified risks associated with tiragolumab in combination with atezolizumab. Based on the mechanism of action of tiragolumab and atezolizumab, additional immune-mediated adverse events are potential overlapping toxicities associated with combination use of tiragolumab plus atezolizumab.

#### Appendix 4: Safety Plan: Management of Identified and Potential Risks

---

Based on clinical experience to date, it is anticipated that immune-mediated adverse events following treatment with tiragolumab and atezolizumab will be amenable to monitoring and manageable in the setting of this combination study. The extensive experience with immune CPIs to date has been incorporated into the design and safety management plan (see Section 5.1) in order to reduce the potential risks to participating participants. Participants with a history of autoimmune disease will be excluded from this study (see Section 5.2). Participants previously treated with approved or experimental CIT will also be excluded from participation in this study.

[REDACTED]

#### **A4-4      ADVERSE EVENTS OF SPECIAL INTEREST (IMMEDIATELY REPORTABLE TO THE SPONSOR)**

Adverse events of special interest are required to be reported by the investigator to the Sponsor immediately (i.e., no more than 24 hours after learning of the event; see Section A3-5 for reporting instructions). Adverse events of special interest for this study are as follows:

- [REDACTED]
- [REDACTED]
- [REDACTED]
- [REDACTED]
- [REDACTED]
- [REDACTED]
- [REDACTED]
- [REDACTED]
- [REDACTED]
- [REDACTED]
- [REDACTED]

#### Appendix 4: Safety Plan: Management of Identified and Potential Risks

---

- [REDACTED]
- [REDACTED]
- [REDACTED]
- [REDACTED]
- [REDACTED]
- [REDACTED]
- [REDACTED]
- [REDACTED]
- [REDACTED]
- [REDACTED]
- [REDACTED]
- [REDACTED]

#### A4–5 RISKS ASSOCIATED WITH ATEZOLIZUMAB AND/OR TIRAGOLUMAB AND GUIDELINES FOR MANAGEMENT OF ADVERSE EVENTS ASSOCIATED WITH TIRAGOLUMAB AND/OR ATEZOLIZUMAB

Toxicities associated or possibly associated with atezolizumab and/or tiragolumab treatment should be managed according to standard medical practice. Additional tests, such as autoimmune serology or biopsies, should be used to evaluate for a possible immunogenic etiology when clinically indicated.

Although most *toxicities* observed with immunomodulatory agents have been mild and self-limiting, *they* should be recognized early and treated promptly to avoid potential major complications. Discontinuation of atezolizumab and/or tiragolumab may not have an immediate therapeutic effect, and in severe cases, immune-mediated toxicities may require acute management with topical corticosteroids, systemic corticosteroids, or other immunosuppressive agents.

Timely and up-to-date information *the risks associated with atezolizumab should be shared with patients and family caregivers prior to initiating atezolizumab and/or tiragolumab. Patients and caregivers should be instructed to have a high level of suspicion that new symptoms are treatment related.*

The following are general recommendations for management of any other adverse events that may occur and are not specifically listed in subsequent subsections.

- [REDACTED]

## Appendix 4: Safety Plan: Management of Identified and Potential Risks

---

- [REDACTED]
- [REDACTED]
- [REDACTED]
- [REDACTED]
- [REDACTED]

[figure not shown]
### A4-5.1 DOSE MODIFICATIONS

There will be no dose modifications for atezolizumab and tiragolumab in this study.

### A4-5.2 TREATMENT INTERRUPTION

Atezolizumab and tiragolumab treatment may be temporarily suspended in participants experiencing toxicity as appropriate for management of toxicity. On the basis of the available characterization of mechanism of action, tiragolumab may cause adverse events similar to but independent of atezolizumab, may exacerbate the frequency or severity of atezolizumab-related adverse events, or may have non-overlapping toxicities with atezolizumab. Because these scenarios may not be distinguished from one another in the clinical setting, immune-mediated adverse events should generally be attributed to atezolizumab and tiragolumab, and dose interruptions or treatment discontinuation in response to immune-mediated adverse events should be applied to atezolizumab and tiragolumab.

[REDACTED]

**A4–5.3      MANAGEMENT GUIDELINES**  
**PULMONARY EVENTS**

Pulmonary events may present as new or worsening cough, chest pain, fever, dyspnea, fatigue, hypoxia, pneumonitis, and pulmonary infiltrates. Participants will be assessed for pulmonary signs and symptoms throughout the study.

All pulmonary events should be thoroughly evaluated for other commonly reported etiologies such as pneumonia or other infection, lymphangitic carcinomatosis, pulmonary embolism, heart failure, COPD, or pulmonary hypertension. COVID-19 evaluation should be performed per institutional guidelines where relevant. Management guidelines for pulmonary events are provided in [Table A4-1](#).

**Table A4-1    Management Guidelines for Pulmonary Events, Including Pneumonitis**

| Event  | Management |
|--|------------|
|  |            |

| Event | Management |
|-------|------------|
|-------|------------|

1. *Journal of the American Medical Association*, 2000; 283: 2639-2644.

d

### HEPATIC EVENTS

Participants eligible for study treatment must have adequate liver function, as manifested by measurements of total bilirubin and hepatic transaminases; liver function will be monitored throughout study treatment. Management guidelines for hepatic events are provided in [Table A4-2](#).

Participants with right upper-quadrant abdominal pain and/or unexplained nausea or vomiting should have liver function tests (LFTs) performed immediately and the results reviewed before administration of the next dose of study drug(s).

For participants with elevated LFTs, concurrent medication, viral hepatitis, and toxic or neoplastic etiologies should be considered and addressed, as appropriate.

**Table A4-2 Management Guidelines for Hepatic Events**

| Event      | Management |
|------------|------------|
| [Redacted] |            |
| a          | [Redacted] |
| b          |            |
| c          |            |

**GASTROINTESTINAL EVENTS**

Management guidelines for diarrhea or colitis are provided in [Table A4-3](#).

All events of diarrhea or colitis should be thoroughly evaluated for other more common etiologies. For events of significant duration or magnitude or associated with signs of systemic inflammation or acute-phase reactants (e.g., increased C-reactive protein, platelet count, or bandemia): Perform sigmoidoscopy (or colonoscopy, if appropriate) with colonic biopsy, with three to five specimens for standard paraffin block to check for inflammation and lymphocytic infiltrates to confirm colitis diagnosis.

**Table A4-3 Management Guidelines for Gastrointestinal Events (Diarrhea or Colitis)**

| Event | Management |
|-------|------------|
|       |            |

| Event | Management |
|-------|------------|
|-------|------------|

[illegible]

C

**ENDOCRINE EVENTS**

Management guidelines for endocrine events are provided in [Table A4-4](#).

Participants with unexplained symptoms such as headache, fatigue, myalgias, impotence, constipation, or mental status changes should be investigated for the presence of thyroid, pituitary, or adrenal endocrinopathies. Participants should be referred to an endocrinologist if an endocrinopathy is suspected. Thyroid-stimulating hormone (TSH) and free triiodothyronine and thyroxine levels should be measured to determine whether thyroid abnormalities are present. Pituitary hormone levels and function tests (e.g., TSH, growth hormone, luteinizing hormone, follicle-stimulating hormone, testosterone, prolactin, adrenocorticotrophic hormone [ACTH] levels, and ACTH stimulation test) and MRI of the brain (with detailed pituitary sections) may help to differentiate primary pituitary insufficiency from primary adrenal insufficiency.

**Table A4-4 Management Guidelines for Endocrine Events**

| Event | Management |
|-------|------------|
|       |            |

**Table A4-4 Management Guidelines for Endocrine Events (cont.)**

| Event | Management |
|-------|------------|
|       |            |

**Table A4-4 Management Guidelines for Endocrine Events (cont.)**

| Event | Management |
|-------|------------|
|       |            |

**Table A4-4 Management Guidelines for Endocrine Events (cont.)**

|   |  |
|---|--|
| a |  |
| b |  |
| c |  |

**OCULAR EVENTS**

An ophthalmologist should evaluate visual complaints (e.g., uveitis, retinal events). Management guidelines for ocular events are provided in [Table A4-5](#).

**Table A4-5 Management Guidelines for Ocular Events**

| Event | Management |
|-------|------------|
| a     |            |
|       |            |
|       |            |
| b     |            |
| c     |            |

## **IMMUNE-MEDIATED CARDIAC EVENTS**

[figure not shown]

### **IMMUNE-MEDIATED MYOCARDITIS**

*Myocarditis symptoms are nonspecific and may occur as early as days or weeks after the first or second dose of atezolizumab with or without tiragolumab.*

Immune-mediated myocarditis should be suspected in any participant presenting with signs or symptoms suggestive of myocarditis, including, but not limited to, laboratory (e.g., troponin, B-type natriuretic peptide) or cardiac imaging abnormalities, dyspnea, chest pain, palpitations, fatigue, decreased exercise tolerance, or syncope. Myocarditis may also be associated with pericarditis (see section on immune-mediated pericardial disorders below) and should be managed accordingly. *Although myocarditis events are rare, myocarditis is often severe and associated with myositis or myasthenia gravis.*

Immune-mediated myocarditis needs to be distinguished from myocarditis resulting from infection (commonly viral, e.g., in a participant who reports a recent history of gastrointestinal illness), ischemic events, underlying arrhythmias, exacerbation of preexisting cardiac conditions, or progression of malignancy.

Participants with signs and symptoms of myocarditis, in the absence of an identified alternate etiology, should be treated according to the guidelines in [Table A4-6](#).

**IMMUNE-MEDIATED PERICARDIAL DISORDERS**

Immune-mediated pericarditis should be suspected in any participant presenting with chest pain and may be associated with immune-mediated myocarditis (see section on immune-mediated myocarditis above).

[REDACTED]

[REDACTED]

[REDACTED]

[REDACTED]

**Table A4-6 Management Guidelines for Immune-Mediated Cardiac Events**

| Event      | Management |
|------------|------------|
| [REDACTED] |            |

**INFUSION-RELATED REACTIONS**

IRRs are known to occur with the administration of monoclonal antibodies and have been reported with tiragolumab/placebo and atezolizumab. These reactions, which are thought to be due to release of cytokines and/or other chemical mediators, occur within 24 hours of tiragolumab/placebo or atezolizumab administration and are generally mild to moderate in severity.

Guidelines for medical management of IRRs are provided in [Table A4-7](#).

**Table A4-7 Management Guidelines for Infusion-Related Reactions**

| Event  | Management |
|--|------------|
| A large rectangular area of the document is completely redacted with a solid black fill. |            |

### Table A4-7 Management Guidelines for Infusion-Related Reactions

a

b

#### Appendix 4: Safety Plan: Management of Identified and Potential Risks

[figure not shown]
---

[REDACTED]

[REDACTED]

#### Appendix 4: Safety Plan: Management of Identified and Potential Risks

---

## PANCREATIC EVENTS

The differential diagnosis of acute abdominal pain should include pancreatitis. Appropriate workup should include an evaluation for ductal obstruction, as well as serum amylase and lipase tests. Management guidelines for pancreatic events, including pancreatitis, are provided in [Table A4-9](#).

**Table A4-9 Management Guidelines for Pancreatic Events, Including Pancreatitis**

| Event | Management |
|-------|------------|
|       |            |

**Table A4-9 Management Guidelines for Pancreatic Events, Including Pancreatitis (cont.)**

| Event      | Management |
|------------|------------|
| [REDACTED] |            |
| a          | [REDACTED] |
| b          |            |
| c          |            |

**DERMATOLOGIC EVENTS**

The majority of cases of rash reported with the use of atezolizumab and/or tiragolumab were mild in severity and self-limiting, with or without pruritus. [REDACTED]

[figure not shown]
[REDACTED]

Management guidelines for dermatologic events are provided in [Table A4-10](#).

**Table A4-10 Management Guidelines for Dermatologic Events**

| Event | Management |
|-------|------------|
|       |            |

[figure not shown]
**Table A4-10 Management Guidelines for Dermatologic Events (cont.)**

|   |  |
|---|--|
| a |  |
| b |  |
| c |  |

**NEUROLOGIC DISORDERS**

Participants may present with signs and symptoms of sensory and/or motor neuropathy. Diagnostic workup is essential for an accurate characterization to differentiate between alternative etiologies. Myasthenia may be associated with myositis (see section on immune-mediated myositis), and patients should be managed accordingly. Management guidelines for neurologic disorders are provided [Table A4-11](#) with specific guidelines for myelitis provided in [Table A4-12](#).

**Table A4-11 Management Guidelines for Neurologic Disorders**

| Event  | Management |
|--|------------|
|  |            |

**Table A4-11 Management Guidelines for Neurologic Disorders (cont.)**

| Event | Management |
|-------|------------|
|       |            |

Table A4-11 Management Guidelines for Neurologic Disorders (cont.)

[figure not shown]
[figure not shown]
|   |  |
|---|--|
| a |  |
| b |  |
| c |  |

Table A4-12 Management Guidelines for Immune-Mediated Myelitis

| Event   | Management |
|---|------------|
|  |            |

**IMMUNE-MEDIATED MENINGOENCEPHALITIS**

Immune-mediated meningoencephalitis should be suspected in any participant presenting with signs or symptoms suggestive of meningitis or encephalitis, including, but not limited to, headache, neck pain, confusion, seizure, motor or sensory dysfunction, and altered or depressed level of consciousness. Encephalopathy from metabolic or electrolyte imbalances needs to be distinguished from potential meningoencephalitis resulting from infection (bacterial, viral, or fungal) or progression of malignancy, or secondary to a paraneoplastic process.

[REDACTED]

Participants with signs and symptoms of meningoencephalitis, in the absence of an identified alternate etiology, should be treated according to the guidelines in [Table A4-13](#).

**Table A4-13 Management Guidelines for Immune-Mediated Meningoencephalitis**

| Event      | Management |
|------------|------------|
| [REDACTED] |            |

**RENAL EVENTS**

[figure not shown]
Eligible participants must have adequate renal function. Renal function, including serum creatinine, should be monitored throughout study treatment. Participants with abnormal renal function should be evaluated and treated for other more common etiologies (including prerenal and postrenal causes, and concomitant medications such as non-steroidal anti-inflammatory drugs). Refer the participant to a renal specialist if clinically indicated. A renal biopsy may be required to enable a definitive diagnosis and appropriate treatment.

Participants with signs and symptoms of nephritis, in the absence of an identified alternate etiology, should be treated according to the guidelines in [Table A4-14](#).

**Table A4-14     Management Guidelines for Renal Events**

| Event | Management |
|-------|------------|
|       |            |

**Table A4-14 Management Guidelines for Renal Events (cont.)**

|   |  |
|---|--|
| a |  |
| b |  |
| c |  |

#### **IMMUNE-MEDIATED MYOSITIS**

Myositis or inflammatory myopathies are a group of disorders sharing the common feature of inflammatory muscle injury; dermatomyositis and polymyositis are among the most common disorders.

|  |  |
|--|--|
|  |  |
|--|--|

Participants with signs and symptoms of myositis, in the absence of an identified alternate etiology, should be treated according to the guidelines in [Table A4-15](#).

**Table A4-15     Management Guidelines for Immune-Mediated Myositis**

| Event | Management |
|-------|------------|
|       |            |

#### Appendix 4: Safety Plan: Management of Identified and Potential Risks

---

[REDACTED]

- [REDACTED]
- [REDACTED]
- [REDACTED]
  - [REDACTED]
  - [REDACTED]
  - [REDACTED]
- [REDACTED]
- [REDACTED]
- [REDACTED]
- [REDACTED]
- [REDACTED]

[REDACTED]

[REDACTED]

[REDACTED]

### **A5–1      PREGNANCIES IN FEMALE PARTICIPANTS**

Female participants will be instructed through the Informed Consent Form to immediately inform the investigator if they become pregnant during the study, within 90 days after the final dose of tiragolumab, and within 5 months after the final dose of atezolizumab. A paper Clinical Trial Pregnancy Reporting Form should be completed and submitted to the Sponsor or its designee immediately (i.e., no more than 24 hours after the investigator becomes aware of the pregnancy), either by faxing or by scanning and emailing the form, using the fax number or email address provided to investigators. Pregnancy should not be recorded on the Adverse Event eCRF. The investigator should discontinue study treatment and counsel the participant, discussing the risks of the pregnancy and the possible effects on the fetus. Monitoring of the participant should continue until conclusion of the pregnancy. Any serious adverse events associated with the pregnancy (e.g., an event in the fetus, an event in the mother during or after the pregnancy, or a congenital anomaly or birth defect in the child) should be reported on the Adverse Event eCRF. In addition, the investigator will submit a Clinical Trial Pregnancy Reporting Form when updated information on the course and outcome of the pregnancy becomes available.

Attempts should be made to collect and report infant health information. When permitted by the site, an Authorization for the Use and Sharing of Infant Health Information would need to be signed by one or both parents (as per local regulations) to allow for follow-up on the infant. If the authorization has been signed, the infant's health status at birth should be recorded on the Clinical Trial Pregnancy Reporting Form. In addition, the Sponsor may collect follow-up information on the infant's health status at 6 and 12 months after birth.

### **A5–2      PREGNANCIES IN FEMALE PARTNERS OF MALE PARTICIPANTS**

Male participants will be instructed through the Informed Consent Form to immediately inform the investigator if a female partner becomes pregnant during the study or within 90 days after the final dose of tiragolumab. The investigator should report the pregnancy on the paper Clinical Trial Pregnancy Reporting Form and submit the form to the Sponsor or its designee immediately (i.e., no more than 24 hours after learning of the pregnancy), either by faxing or by scanning and emailing the form using the fax number or email address provided to investigators. Attempts should be made to collect and report details of the course and outcome of any pregnancy in the partner of a male participant exposed to study treatment. When permitted by the site, the pregnant partner would need to sign an Authorization for Use and Sharing of Pregnancy Health Information to allow for follow-up on her pregnancy. If the authorization has been signed, the investigator should submit a Clinical Trial Pregnancy

## **Appendix 5: Collection of Pregnancy Information**

---

Reporting Form with additional information on the pregnant partner and the course and outcome of the pregnancy as it becomes available.

Attempts should be made to collect and report infant health information. When permitted by the site, an Authorization for the Use and Sharing of Infant Health Information would need to be signed by one or both parents (as per local regulations) to allow for follow-up on the infant. If the authorization has been signed, the infant's health status at birth should be recorded on the Clinical Trial Pregnancy Reporting Form. In addition, the Sponsor may collect follow-up information on the infant's health status at 6 and 12 months after birth.

An investigator who is contacted by the male participant or his pregnant partner may provide information on the risks of the pregnancy and the possible effects on the fetus, to support an informed decision in cooperation with the treating physician and/or obstetrician.

### **A5-3      ABORTIONS**

A spontaneous abortion in a female participant exposed to study treatment (or the female partner of a male participant exposed to study treatment) should be classified as a serious adverse event (as the Sponsor considers abortions to be medically significant), recorded on the Adverse Event eCRF, and reported to the Sponsor immediately (i.e., no more than 24 hours after the investigator becomes aware of the event; see Section [A3-5](#)).

If a therapeutic or elective abortion was performed because of an underlying maternal or embryofetal toxicity, the toxicity should be classified as a serious adverse event, recorded on the Adverse Event eCRF, and reported to the Sponsor immediately (i.e., no more than 24 hours after the investigator becomes aware of the event; see Section [A3-5](#)). A therapeutic or elective abortion performed for reasons other than an underlying maternal or embryofetal toxicity is not considered an adverse event.

All abortions should be reported as pregnancy outcomes on the paper Clinical Trial Pregnancy Reporting Form.

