#### **8.3.5 Pregnancy**

Female participants of childbearing potential will be instructed through the ICF to immediately inform the investigator if they become pregnant during the study, within 90 days after the final dose of tiragolumab/placebo, and within 5 months after the final dose of atezolizumab.

Male participants will be instructed through the ICF to immediately inform the investigator if a female partner becomes pregnant during the study or within 90 days after the final dose of tiragolumab/placebo.

If a pregnancy is reported, the investigator should inform the Sponsor within 24 hours of learning of the pregnancy and should follow the procedures outlined in [Appendix 5](#).

All pregnancies reported during the study should be followed until pregnancy outcome, with follow-up information on the infant collected according to procedures outlined in [Appendix 5](#). The Sponsor or a designee may follow up by telephone, fax, email, and/or a monitoring visit to obtain additional case details and outcome information (e.g., from hospital discharge summaries, consultant reports, autopsy reports) in order to perform an independent medical assessment of the reported case.

Abnormal pregnancy outcomes (e.g., spontaneous abortion, fetal death, stillbirth, congenital anomalies, ectopic pregnancy) are considered serious adverse events.

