### **A3–1        DEFINITION OF ADVERSE EVENT**

#### **Adverse Event Definition**

An adverse event is any untoward medical occurrence in a participant or clinical study participant temporally associated with the use of a study treatment, whether or not considered related to the study treatment.

Note: An adverse event can therefore be any unfavorable and unintended sign (including an abnormal laboratory finding), symptom, or disease (new or exacerbated) temporally associated with the use of study intervention.

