#### **A3–2      DEFINITION OF SERIOUS ADVERSE EVENT**

If an event is not an adverse event per the definition in Section [A3–1](#), it cannot be a serious adverse event even if serious conditions are met (e.g., hospitalization for signs or symptoms of the disease under study, death due to progression of disease).

A serious adverse event is defined as any untoward medical occurrence that, at any dose:

- Results in death
- Is life threatening

The term "life-threatening" in the definition of "serious" refers to an event in which the participant was at risk of death at the time of the event. It does not refer to an event that hypothetically might have caused death if it were more severe.

- Requires inpatient hospitalization or prolongation of existing hospitalization

In general, hospitalization signifies that the participant has been detained (usually involving at least an overnight stay) at the hospital or emergency ward for observation and/or treatment that would not have been appropriate in the physician's office or outpatient setting. Complications that occur during hospitalization are adverse events. If a complication prolongs hospitalization or fulfills any other seriousness criteria, the event is serious. When in doubt as to whether "hospitalization" occurred or was necessary, the adverse event should be considered serious.

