### **A5-4      ABNORMAL PREGNANCY OUTCOMES**

Abnormal pregnancy outcomes (e.g., spontaneous abortion, fetal death, stillbirth, congenital anomaly, birth defect, ectopic pregnancy) in a female participant exposed to study treatment (or the female partner of a male participant exposed to study treatment) should be classified as a serious adverse event, recorded on the Adverse Event eCRF, and reported to the Sponsor immediately (i.e., no more than 24 hours after the investigator becomes aware of the event; see Section [A3-5](#)).

## Appendix 6

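### Appendix 5 classes a pregnancy loss in a male participant's partner as a serious adverse event, against the protocol's own definitions, and Section 9.3.2.1 shows no rule to keep it out of his arm's count

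*Combined protocol and SAP*

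**What the plan says.** Appendix 5, A5-3, addresses a spontaneous abortion in a female participant "or the female partner of a male participant exposed to study treatment) should be classified as a serious adverse event". The reason and route follow: "as the Sponsor considers abortions to be medically significant), recorded on the Adverse Event eCRF, and reported to the Sponsor immediately". A5-4 extends this to fetal death, stillbirth, congenital anomaly, birth defect and ectopic pregnancy, again in a participant or a male participant's partner; each "should be classified as a serious adverse event, recorded on the Adverse Event eCRF, and reported to the Sponsor immediately". Section 8.3.5 says abnormal outcomes ("e.g., spontaneous abortion, fetal death, stillbirth, congenital anomalies, ectopic pregnancy) are considered serious adverse events") without saying whose pregnancy is meant.

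Appendix 3 defines the terms more narrowly. A3-1: "An adverse event is any untoward medical occurrence in a participant or clinical study participant temporally associated with the use of a study treatment". A3-2 opens by saying that if an event is not an adverse event under A3-1, "it cannot be a serious adverse event even if serious conditions are met".

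On analysis, Table 2 makes incidence and severity of adverse events the only endpoint. Table 5 defines the safety analysis set as participants exposed to study treatment. Section 9.3.2.1 summarises all adverse events and all serious adverse events that start or worsen on or after first dose. Section 9.3 says that no SAP will be provided.

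**The concern.** A participant's partner is not a participant. Under Appendix 3 her miscarriage is not an adverse event and so cannot be a serious one. Under Appendix 5 the site must classify it as serious and enter it on the Adverse Event eCRF. Both instructions are in force, and a site cannot satisfy both.

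The consequence is statistical. The study's single endpoint is a count of participants with adverse events by type and grade. A record of an event in someone who was never treated, held under a treated man's number, looks to a tabulation program like any other treatment-emergent serious event. With arms of about 30, one such record is visible in a summary table.

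**Working it through.** **Step 1: the definitions side by side.**

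| Place | Whose event | Status and form |
|---|---|---|
| A3-1, A3-2 | Participant only | Anything else is not an adverse event and cannot be serious |
| A5-1 | Female participant; also fetus or child | Serious events associated with the pregnancy go on the Adverse Event eCRF |
| A5-2 | Partner of a male participant | Paper pregnancy form; follow-up needs the partner's signed authorization |
| A5-3, A5-4 | Female participant or partner of a male participant | Serious adverse event, on the Adverse Event eCRF |
| 8.3.5 | Not stated | Serious adverse event |

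For the partner, A3-1/A3-2 and A5-3/A5-4 give opposite answers. A3-2 does list congenital anomaly or birth defect as a seriousness criterion, but its opening condition still requires an event that meets A3-1.

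**Step 2: from the form to the table.** The partner has no participant number, so the record would sit under the man's. The inclusion rule visible in Section 9.3.2.1 is timing relative to first dose. His partner's event, arising after his first dose, meets it. Table 5 restricts which people are in the analysis set, and the man is in it. No visible sentence says that a record about someone else is dropped. Part of that section is redacted, so the statement is limited to what can be read.

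**Step 3: size.** The documents give no figure on this point to reproduce. Inputs for scale: about 60 participants (Section 1.1) and 1:1 randomisation (Section 4.1).

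- Arm size: 60 / 2 = 30.
- Maximum change in any-serious-event incidence per record: 1/30 = 3.3 percentage points, if the man has no other serious event.
- Minimum: 0, if he already has one, because incidence counts participants.
- If actual enrolment differs (assumed values): 1/20 = 5.0 points at 40 participants; 1/40 = 2.5 points at 80.
- Appendix 1 (A1-5) still gives approximately 1150 participants, which does not match Section 1.1. At that size one record would be 1/575 = 0.17 points.

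**Step 4: average change, for illustration.** If p is the probability that the man already has a serious event, independent of the partner's outcome, the expected change is (1/30) × (1 − p). Section 2.2.2 gives serious-event rates of 41.2% and 52.2% in the two arms of the Phase II CITYSCAPE study, in advanced disease; carrying them over to this adjuvant population is an assumption.

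- p = 0.412: 0.588 / 30 = 2.0 points.
- p = 0.522: 0.478 / 30 = 1.6 points.

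For incidence of any adverse event (97.1% and 98.5% in that study) the same formula gives 0.029 / 30 = 0.10 and 0.015 / 30 = 0.05 points, which is negligible.

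**The case against.** The best defence is that Appendix 5 is a deliberate, specific extension for rapid safety reporting. It names partners in both A5-3 and A5-4, Section 8.3.5 is not limited to female participants, and A5-1 already sends events in a fetus or child to the Adverse Event eCRF. The examples beside the opening condition in A3-2 concern the disease under study, not pregnancy. This stands as a reason to notify the sponsor promptly. It does not make the partner's event one of the man's own adverse events, and neither appendix says which prevails.

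A second objection is that no sentence says the record will be tabulated. That is correct. A reader might infer that partner events will certainly appear in the primary safety tables, and the documents do not support that: Table 5 covers exposed participants only, and a programmer could drop the record. A pregnancy-loss term under a male participant would also be easy to recognise. The supported statement is that the record counts unless someone filters it, and no visible rule tells them to.

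A third is practical weight. Section 5.1 requires men with partners of childbearing potential to abstain or use condoms, Section 9.1 says no hypothesis is tested, and such events should be rare. All of this stands and keeps the point minor.

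A reader might also infer unequal ascertainment by arm. A5-2 asks a man to report if a partner "becomes pregnant during the study or within 90 days after the final dose of tiragolumab", while Section 8.3.5 has "becomes pregnant during the study or within 90 days after the final dose of tiragolumab/placebo"; with treatment unblinded, a comparator-arm man has no tiragolumab dose from which to count. The inference is not established. The study period itself counts in both versions, and participation lasts until safety follow-up is complete (Section 1.1). Section 8.3.5 already names placebo. Adverse event collection under Section 8.3.1 runs from the final dose of study treatment in either arm. What remains is a wording mismatch.

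**Conclusion.** The point holds and is wrong as written, though minor. A5-3 and A5-4 contradict A3-1 and A3-2 on whether an event in a male participant's partner can be a serious adverse event, and the visible analysis text would count it as his unless it is removed. The size is at most 3.3 percentage points of any-serious-event incidence per record in an arm of about 30, and zero if the man already has a serious event; 3.3 is a ceiling, not a fixed increment. This rests on approximately 60 participants, 1:1 allocation, all participants treated, and the record being held under the man's number. The expected number of such events cannot be derived from the documents. No difference in ascertainment between arms is shown.

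**What to change.** 1. Leave the 24-hour reporting route to the sponsor unchanged, including entry through the eCRF and the electronic data capture system. Dropping the eCRF entry would remove the electronic route to the sponsor's safety group.
2. Add a flag to the record for outcomes in a partner or an infant.
3. Reconcile A5-3, A5-4 and Section 8.3.5 with A3-1 and A3-2, for example by saying that partner and infant outcomes are reported under serious adverse event procedures without being adverse events of the participant.
4. State in Section 9.3.2.1 that flagged outcomes are listed separately and not counted in participants' adverse event or serious adverse event incidence. A female participant's own pregnancy loss remains her event.
5. Separately, reconcile the wording of the partner-pregnancy window in A5-2 and Section 8.3.5.

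The cost is a few sentences and one field on the record. With no SAP planned, the tabulation rule has to go in the protocol.
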